## 1.0 Objectives

### 1.1 Study Rationale

Our primary goal is to conduct a pilot study of a population-specific psychological intervention aimed at decreasing anxiety and promoting coping in caregivers of patients with malignant gliomas. **In this initial phase of the research, we will pilot the intervention with 25 malignant glioma caregivers in order to assess feasibility and acceptability of the intervention.**

### 1.2 Specific Aims

- 1) To refine a caregiver-directed intervention and study protocol based on acceptability feedback from an open pilot study with exit interviews.

## 2.0 Background

### 2.1 Introduction

Malignant gliomas are the most common types of brain tumors and have a disease course characterized by high symptom burden and rapid cancer progression. Survival of patients with glioblastoma, the most common type of malignant glioma, is on the order of 15 months, even in patients treated aggressively with chemotherapy and radiation. Thus, a diagnosis of malignant glioma has a significant impact on a patient's family and friends ("caregivers"). There is increasing recognition that caregivers who experience substantial distress related to their loved one's serious medical illness have worse physical and psychological health, which also may negatively impact the patient's health and outcomes. Caregivers of patients with brain tumors face significant challenges due to the impact of the cancer on the patients' central nervous system. Specifically, these caregivers must cope with their loved one's progressive cognitive decline, personality and behavior changes, and accumulation of neurological deficits as the disease progresses. This is physically, financially and emotionally draining, and caregivers of patients with malignant gliomas experience poor quality of life and high rates of psychological distress. We conducted a prospective study of patients with newly diagnosed malignant glioma and their caregivers (DF/HCC 15-500), with preliminary results demonstrating that **more than 50% of caregivers had clinically significant anxiety at the time of their loved one's diagnosis, with almost two-thirds endorsing anxiety over their course of illness.** Despite the high rates of distress in caregivers of patients with malignant gliomas, few interventions have been developed to address the unique supportive care and coping needs of this highly burdened caregiver population.

**The goal of this proposal is to pilot a population-specific psychological intervention aimed at decreasing anxiety and promoting coping in caregivers of patients with malignant gliomas.** Our intervention is based on a conceptual framework for caregiver-directed interventions developed by our multi-disciplinary team. We recently used this framework to develop an intervention for caregivers of patients undergoing bone marrow transplantation, which was highly acceptable and beneficial to caregivers who participated in the open pilot study. While the proposed intervention is based upon this framework, we have used qualitative data collected from caregivers of patients with malignant glioma

(DF/HCC 15-500 and DF/HCC 18-171) to refine the intervention and ensure that it is targeted to the specific needs of this caregiver population. Our study population will include caregivers within the first six months of their loved one's diagnosis with malignant glioma who report clinically significant anxiety. We opted to enroll caregivers with clinically significant anxiety as they are in greatest need of a behavioral intervention focused on their distress and concerns about their loved one's health and diagnosis. Enrolled caregivers will participate in six weekly, cognitive-behavioral therapy-based, individual sessions with a mental health clinician, designed to provide them with the strategies and coping skills to manage the distress related to their loved one's illness. Findings from this project may inform the development of a future randomized efficacy trial to demonstrate the impact of the intervention on caregivers' psychological outcomes, coping, and well-being.

### 3.0 Inclusion and Exclusion Criteria

The population for this study will include English-speaking adults (age  $\geq 18$ ) who are the primary caregiver for an individual diagnosed with a malignant glioma within the past 6 months and present for cancer care at the Massachusetts General Hospital Cancer Center, Boston, MA. The caregiver must also have at least mild anxiety symptoms, defined as a 7-Item Generalized Anxiety Disorder (GAD-7) score of 5 or greater. See Table 1 for a summary of study inclusion/exclusion criteria:

Table 1. Study Inclusion/Exclusion Criteria

Inclusion Criteria	Exclusion Criteria
Age $\geq 18$	Deemed inappropriate for the study by the patient's clinician or the study PI
Identified by a patient with a malignant glioma (WHO Grade III or IV glioma) as the patient's primary caregiver	
The patient is receiving care at the MGH Cancer Center	
The patient was diagnosed with a malignant glioma within the past 6 months	
Able to speak and read in English	
Generalized Anxiety Disorder 7-item (GAD-7) score $\geq 5$	
Participants may or may not be pregnant.	

Rationale for inclusion/exclusion: This research is focused on developing an intervention for caregivers with malignant gliomas. Only participants within 6-months of their loved one's brain tumor diagnosis are eligible to participate, as the intervention is targeted at the stressors caregivers may face during this time. Participants must be able to speak and read in English as we do not have the resources to conduct the intervention in additional languages. Participants must report clinically significant anxiety symptoms, defined as a Generalized Anxiety Disorder Scale (GAD-7) score  $\geq 5$ , as our intervention intends to address anxiety symptoms in caregivers. Caregivers deemed inappropriate for the study by the patient's clinician or the study PI will be ineligible to participate. Pregnant women will be included in the study. Adults unable to consent, individuals who are not yet adults, and prisoners will not be included.

#### Screening for eligibility

Study staff will review the outpatient clinic schedule for the Yawkey 9E Brain Tumor Clinic to identify patients with malignant gliomas. To facilitate identification of potential participants and assess eligibility, study staff will review minimum necessary medical record data via a HIPAA waiver. This will ensure that caregivers are potentially eligible to participate in the study prior to contacting them to obtain informed consent. Prior to contacting potential participants identified via screening, the patient's primary treating oncologist will be contacted to inform them that we plan to approach the patient's caregiver for study participation and to inquire about any concerns regarding study participation. If clinicians have specific concerns about the appropriateness of enrolling a particular caregiver, we will not contact that caregiver.

#### **4.0 Study-Wide Number of Subjects**

N/A

#### **5.0 Study-Wide Recruitment Methods**

N/A

#### **6.0 Multi-Site Research**

N/A

#### **7.0 Study Timelines**

As this cognitive-behavioral therapy-based intervention consists of 6 weekly or biweekly sessions with a mental health clinician, an individual subject will participate for approximately 6 to 12 weeks. We anticipate that all study subjects will be enrolled within 18 months and that the study will be complete by January 2020.

#### **8.0 Study Endpoints**

The primary endpoint of this study is feasibility of the intervention. In an exploratory analysis, we will examine preliminary efficacy of the intervention in improving caregiver-reported outcomes from baseline to post-intervention.

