### *9.3 Registration*

Study staff will register eligible participants in the Clinical Trials Management System (CTMS) OnCore as required by DF/HCC SOP REGIST-101 after the participant completes the brief enrollment survey. Caregivers who report GAD-7 scores  $<5$  will be considered ineligible for the study and will not be registered in OnCore. If a caregiver's GAD-7 score renders them ineligible but they are still interested in the study, we will re-approach them in 3 months to re-administer the GAD-7. Caregivers who do not complete the brief enrollment survey will not be registered in OnCore.

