### *9.4 Study design*

This study will be a prospective, single-arm pilot study to assess feasibility and acceptability of a psychological intervention for caregivers of patients with malignant gliomas. We will use qualitative data to refine a multicomponent psychological intervention specifically targeting the needs of caregivers of patients with malignant gliomas who are within the first 6 months of diagnosis. We will collect demographics at baseline and will ask caregivers to complete a questionnaire pre- and post-intervention to assess caregivers' self-reported information about mood, caregiver burden, coping, quality of life and illness understanding.

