## **11.0 Data Management and Confidentiality**

### *11.1 Sample size and power calculations*

We will recruit and consent 25 caregivers for the open pilot. We chose the sample size of 25 caregivers based on the feasibility of completing the project in a timely fashion, given the rarity of this disease. It is

expected that it will take approximately twelve to eighteen months to complete accrual for the study. The proposed sample size is also sufficient to provide us with preliminary data that can be utilized to determine the effect size and adequately power a multi-center randomized controlled trial in the future.

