## **23.0 Local Number of Subjects**

A total of 25 subjects (excluding screen failures) will be accrued locally. We expect more than 50% to demonstrate at least mild anxiety (GAD-7 score of 5 or greater) so total accrual of no more than 50 caregivers including screen failures should be necessary.

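### A pre-post change in a single arm selected for raised anxiety should be reported as uncontrolled change, not as preliminary efficacy, and should not supply the next trial's effect size

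*Combined protocol and SAP*

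**What the plan says.** - **Design and size.** Section 9.4: "This study will be a prospective, single-arm pilot study". Section 11.1: "We will recruit and consent 25 caregivers for the open pilot".
- **Selection.** Section 3.0: "The caregiver must also have at least mild anxiety symptoms". The rationale in the same section restates this as "Participants must report clinically significant anxiety symptoms, defined as a Generalized Anxiety Disorder Scale (GAD-7) score" of 5 or more. For interested caregivers below the cut, section 9.3 adds "we will re-approach them in 3 months to re-administer the GAD-7"; section 9.7 repeats the re-test.
- **Measurement.** The table in section 11.3 puts the GAD-7 at screening only. HADS, CarGOQoL, CRA, CASE and MOCS are taken before and after the intervention. No interval between the screening GAD-7 and the pre-intervention HADS is given. Section 7.0 puts participation at about 6 to 12 weeks.
- **Analysis.** Section 8.0 makes feasibility primary and adds an exploratory analysis: "we will examine preliminary efficacy of the intervention in improving caregiver-reported outcomes from baseline to post-intervention". Section 11.2 names paired t-tests and gives neither alpha nor sidedness.
- **Use.** Section 11.1 says the data can serve to determine an effect size and power a multi-center randomized trial.
- **Earlier cohort.** Section 2.1 reports a prospective caregiver study, 15-500, with anxiety rates at diagnosis and over the illness. It appears as background and as a source for the intervention's content, not as a reference for change.

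Regression toward the mean, natural course and expected change without the program are not mentioned anywhere.

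**The concern.** A paired t-test against zero asks whether scores moved. It answers a question about efficacy only if scores would have stayed put without the program. Two features make that doubtful here.

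First, people are let in on a raised reading of one self-report anxiety scale and then followed on another. The GAD-7 looks back 2 weeks and the HADS 1 week, so a temporary high at screening can carry into the pre-intervention HADS and fade by the post-intervention one. The re-test at 3 months gives some caregivers a second chance to enter on a high reading.

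Second, the caregivers' situation is itself changing in the months after diagnosis. Adaptation could lower distress and the patient's decline could raise it.

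A significant fall could therefore be read as a signal of efficacy when part or all of it is not. If the observed change is then used as the effect size for a randomized trial, that trial could be too small.

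**Working it through.** **The plan's own figure.** The only stated number that bears on the selection is in section 23.0: no more than 50 caregivers including screen failures, from 25 eligible and more than 50% above the cut. 25 / 0.50 = 50, which reproduces. The paired tests have no stated power, alpha, SD or effect size.

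**Assumptions (not in the documents).** Two-sided 5% test, so 2.5% in the direction of improvement; HADS-anxiety SD 4; pre-post HADS correlation 0.6; normal scores; no treatment effect and no time trend. The share above the cut runs from 50% (section 23.0 expects more) to 66% (section 2.1 reports almost two-thirds with anxiety at some time in the illness). r_pre and r_post are the correlations of the screening GAD-7 with pre- and post-intervention HADS anxiety.

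**Formulas.** With a share p above the cut at standard normal point z:
- mean GAD-7 z-score of those selected: L = φ(z)/p. For 50%, 0.399/0.50 = 0.798; for 66%, 0.366/0.66 = 0.555.
- remaining GAD-7 variance: V = 1 + zL − L². For 50%, 0.363; for 66%, 0.463.
- expected fall = (r_pre − r_post) × L × SD.
- variance of change, in SD² units = 2(1 − 0.6) − (r_pre − r_post)² × (1 − V).

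**Worked case: 0.75 pre, 0.45 post, 50% above the cut.** Fall = 0.30 × 0.798 × 4 = 0.96 points, or 0.239 SD. Variance of change = 0.80 − 0.09 × 0.637 = 0.743, so its SD is 0.862. Standardized change = 0.239 / 0.862 = 0.278. With 25 pairs the noncentrality is 0.278 × 5 = 1.39, and the chance that t exceeds 2.064 is about 26%. Simulation from the truncated normal model agrees.

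| r_pre / r_post | Fall, 50% above | False improvement | Fall, 66% above | False improvement |
|---|---|---|---|---|
| 0.70 / 0.70 | 0 | 2.5% | 0 | 2.5% |
| 0.70 / 0.65 | 0.16 | 4% | 0.11 | 3.5% |
| 0.70 / 0.60 | 0.32 | 6% | 0.22 | 5% |
| 0.70 / 0.50 | 0.64 | 14% | 0.44 | 9% |
| 0.75 / 0.45 | 0.96 | 26% | 0.67 | 15% |

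With 18 pairs (about 70% completing, assumed) the range is 2.5% to 20%.

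**How extreme is the last row?** 0.75 × 0.60 = 0.45, so it supposes that the screening GAD-7 says nothing about the post-intervention HADS beyond what the pre-intervention HADS already says. A still larger rate, 34%, comes from 0.80 / 0.50 with a pre-post correlation of 0.70. There 0.80 × 0.70 = 0.56 exceeds 0.50, so at a given pre-intervention HADS a higher screening GAD-7 would have to predict a lower later score. I leave that case out.

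**Does the bias reach significance by itself?** With 25 pairs the test needs an observed standardized change of 2.064 / 5 = 0.41. The largest expected value above is 0.278. The bias raises the false-positive rate but does not, on average, produce significance unaided.

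**Effect on a later trial (illustrative).** Per-arm size is about 2 × (1.96 + 0.84)² / d² = 15.68 / d². A true effect of 0.3 SD needs 15.68 / 0.09, about 175 per arm. Read as 0.5 SD, it gives 15.68 / 0.25, about 63. A bias of 0.2 SD corresponds to 0.75 / 0.50 with 50% above the cut: 0.25 × 0.798 = 0.20.

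**The case against.** Much can be said for the plan. The analysis is labelled exploratory, feasibility is primary, and section 2.1 leaves efficacy to a future randomized trial. The cut is mild and most caregivers are expected to meet it, so selection is weak. The tested scale is not the selection scale, and section 11.3 lists screening and pre-intervention as separate occasions. All of this stands, and it keeps the point small. It does not supply a reason to take zero as the expected change, and the exploratory label does not cover the use in section 11.1.

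Four stronger readings are tempting but go beyond the documents:

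- *Caregivers enter at a temporary peak, so HADS anxiety will fall.* An unstated gap between GAD-7 and HADS is not a short gap. If the two correlations are equal there is no bias, and change over time could go either way.
- *The stated 5% error is broken.* No error level is stated; 5% is an assumption made here.
- *The sponsor holds an untreated control cohort.* The documents do not call the 15-500 caregivers untreated and do not give their number, scale or visit times.
- *A formal test against 15-500 is the remedy.* Even with an ideal match, the 95% CI half-width for the difference, 1.96 × 0.872 × √(1/25 + 1/m) with the SD of change from the 0.75 / 0.50 case, is 0.48 SD for m = 25 and 0.38 SD for m = 100 (m assumed). Both exceed the largest bias in the table, 0.24 SD.

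The arithmetic also covers HADS anxiety only. The bias should be weaker for depression, quality of life, burden, self-efficacy and coping, which are less close to the selection scale.

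**Conclusion.** The concern holds in limited form. An uncontrolled pre-post change in caregivers selected on anxiety cannot be read as efficacy, because regression toward the mean and natural course are mixed into it and the plan has no reference for either. For HADS anxiety, the spurious fall from selection is 0 to about 1.0 point. The chance of a false improvement is 2.5% with equal correlations, 3.5% to 6% where they differ by 0.05 to 0.10, and about 26% only at the extreme. These figures rest on the assumed alpha, SD and correlations and on the 50% to 66% share above the cut; the documents cannot narrow them. The feasibility conclusion is untouched. Severity is minor, and the main reason to act is the intended use of the change as an effect size.

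**What to change.** - **Sections 8.0 and 11.2:** replace the preliminary-efficacy wording and the test against zero with the mean change and its 95% CI for each scale, labelled as uncontrolled *change during the program*. Name regression toward the mean and natural course as alternative explanations.
- **Section 11.1:** state that the future trial's effect size will not be taken from this uncontrolled change.
- **Optional:** if 15-500, whose caregivers were not given this program, has a compatible scale, anxiety threshold and 6 to 12 week interval, show its change alongside as a descriptive reference, without a formal test.

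The first two changes cost only wording. The third is a short analysis of a study the sponsor has already done, if the data fit. The price is a less favourable-looking result and, where it is used, a reference that is non-concurrent and imprecise.

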#### **9.0 Procedures Involved**

##### *9.1 Recruitment*

Study staff will review the outpatient clinic schedule for the Yawkey 9E Brain Tumor Clinic to identify patients with malignant gliomas. To facilitate identification of potential participants and assess eligibility, study staff will review minimum necessary medical record data via a HIPAA waiver. This will ensure that caregivers are potentially eligible to participate in the study prior to contacting them to obtain informed consent. Prior to contacting potential participants identified via screening, the patient's primary treating oncologist will be contacted to inform them that we plan to approach the patient's caregiver for study participation and to inquire about any concerns regarding study participation. If clinicians have specific concerns about the appropriateness of enrolling a particular caregiver, we will not contact that caregiver.

##### *9.2 Enrollment*

A member of study staff (e.g. PI, Research Assistants) will obtain informed consent in person prior to initiating any study measures. Participants will be consented next time they are in clinic. Research

assistants, all of whom previously have received CITI and consent training, will be provided study-specific recruitment training. Caregivers who would like more time to consider participation at in-clinic approach are able to take the consent forms home with them to review. Caregivers will be provided with study staff contact information if any questions or concerns regarding the research arise.

### *9.3 Registration*

Study staff will register eligible participants in the Clinical Trials Management System (CTMS) OnCore as required by DF/HCC SOP REGIST-101 after the participant completes the brief enrollment survey. Caregivers who report GAD-7 scores  $<5$  will be considered ineligible for the study and will not be registered in OnCore. If a caregiver's GAD-7 score renders them ineligible but they are still interested in the study, we will re-approach them in 3 months to re-administer the GAD-7. Caregivers who do not complete the brief enrollment survey will not be registered in OnCore.

### *9.4 Study design*

This study will be a prospective, single-arm pilot study to assess feasibility and acceptability of a psychological intervention for caregivers of patients with malignant gliomas. We will use qualitative data to refine a multicomponent psychological intervention specifically targeting the needs of caregivers of patients with malignant gliomas who are within the first 6 months of diagnosis. We will collect demographics at baseline and will ask caregivers to complete a questionnaire pre- and post-intervention to assess caregivers' self-reported information about mood, caregiver burden, coping, quality of life and illness understanding.

### *9.5 Selection of Instruments*

#### **9.5.1 7-Item Generalized Anxiety Disorder (GAD-7)**

The GAD-7 ([Appendix 31.01](#)) is a valid self-report measure for assessing generalized anxiety in patients with cancer. Patients indicate how often they have been bothered by symptoms over the last 2 weeks using a likert-type scale ranging from 0 (Not at all) to 3 (Nearly every day). Scores of 5 to 9 are categorized as mild anxiety, scores of 10 to 14 as moderate anxiety, and scores of 15 or greater as severe anxiety. Patients with scores  $\geq 5$  on the GAD-7 (mild symptomatology) will be eligible for participation. The estimated time for completing this scale is 1-3 minutes.

#### **9.5.2 Hospital Anxiety and Depression Scale (HADS)**

We will use the Hospital Anxiety and Depression Scale (HADS) to assess symptoms of depression and anxiety in all study participants. The HADS is a 14-item questionnaire that contains two 7-item subscales assessing depression and anxiety symptoms during the past week ([Appendix 31.02](#)). Used extensively in samples of patients with cancer and their caregivers, the questionnaire consists of a four-point item response format that quantifies the degree to which participants experience mood symptoms. Scores on each subscale range from 0 to 21, with a cutoff of 8 or greater denoting clinically significant anxiety or depression. The estimated time for completing this scale is 2-5 minutes.

#### **9.5.3 Brief Demographic Survey**

This includes self-reported information about participants' gender, race, ethnicity, religion, education, relationship status, household members, employment status, relationship to the patient, and years they have known the patient. It is estimated that these questions ([Appendix 31.03](#)) will take approximately 1-3 minutes to complete.

